8.3.3. MS Treatments and Concomitant Medications

- Plegridy prescription information, including prescribed dose, dosing frequency, start and stop dates, reason for discontinuation (if applicable).
- Use of all concomitant medications (e.g., prescription information, including prescribed dose, dosing frequency, start and stop dates, reason for discontinuation [if applicable]) during follow up.

Refer to Section 16.1 for the timing of assessments.

8.3.4. Laboratory Assessments

The following laboratory assessments will be collected, if performed consistent with routine clinical practice:

- CBC with differential

CONFIDENTIAL

The information contained herein may not be used, disclosed, or published without the written consent of Biogen MA Inc.

- Other laboratory tests recommended in local label (e.g., liver and renal function tests, urinalysis)

Refer to Section 16.1 for the timing of assessments.

8.3.5. Safety

The following assessments will be collected to evaluate the safety of Plegridy:

- SAEs
- AEs of special interest
 - FLS (e.g., chills, body aches, pyrexia, myalgia, or muscle aches)
 - ISRs (e.g., injection site erythema, pain, pruritus, or edema)
- AEs, including laboratory abnormalities, leading to treatment discontinuation

Refer to Section 16.1 for the timing of assessments.

8.3.6. Effectiveness

The following clinical tests/assessments will be collected to evaluate the effectiveness of Plegridy, if performed under routine clinical practice:

- MS relapse information (e.g., date of onset, date of visit, neurologic examination, duration, new and/or recurrent neurologic symptoms, hospitalization, treatments including steroids), if applicable. For the purposes of this study, relapse is defined as new or recurrent neurologic symptoms not associated with fever, lasting at least 24 hours. New or recurrent neurologic symptoms that evolve gradually over months are to be considered disease progression, not an acute relapse. New or recurrent neurological symptoms that occur fewer than 30 days following the onset of a relapse as defined above are to be considered part of the same relapse.
- EDSS information (including Functional System Scores and Ambulation scores), based on neurological examination, when collected as part of routine clinical practice (i.e. not specifically performed for the study).
- Neurologic assessment, if EDSS is not used in routine clinical practice.
- [REDACTED]
- [REDACTED]
- Details of MS-related hospitalizations (e.g., dates of admission and discharge, reason for admission)
- MRI results (e.g., lesion counts, new lesions/ no new lesions), if available
- Ambulation status during follow-up

Refer to Section 16.1 for the timing of assessments.

CONFIDENTIAL

The information contained herein may not be used, disclosed, or published without the written consent of Biogen MA Inc.

8.3.7. Patient-Reported and Health Economics Outcomes

Patient assessment of the following outcome measures will be collected, if consistent with local regulations:

- Impression of functional health and well-being using the EQ-5D-3L index score and the five individual component scores. Refer to Section 16.2, Appendix 1.
- FLS Assessment: Patients will assign a score from “0” to “3” to their muscle aches, chills, fatigue, and body temperature as follows: “0” for absent; “1” for mild, did not interfere with daily activities; “2” for moderate, sufficient to interfere with daily activities; and “3” for severe, bed rest required. Refer to Section 16.3, Appendix 2.

FLS-VAS: This patient-reported assessment includes two VAS ratings and will be performed to evaluate any prophylactic regimen such as acetaminophen, ibuprofen, aspirin, or naproxen used to alleviate FLS. The first VAS will assess the effectiveness of the prophylactic regimen used by the patient to control FLS. Patients will rate their prophylactic regimen to control FLS between “not effective” to “very effective”. The second VAS will evaluate the patient’s satisfaction with the effectiveness of the prescribed regimen to control FLS. Patients will rate their satisfaction from “not satisfied” to “very satisfied.” Refer to Section 16.7, Appendix 6.

Note: If a patient selects “Absent” for Question 1 of the FLS Assessment, then the FLS-VAS does not need to be completed for that patient.

- Healthcare resource consumption questionnaire: This patient-reported questionnaire will ask patients to report the frequency of MS-related, non-MS-related, relapse-related hospitalizations, MS-related neurological visits, MS-related ER visits, and visits to other health care professionals for MS-related and other reasons. Refer to Section 16.4, Appendix 3.
- Treatment adherence questionnaire: This is a patient-reported questionnaire that measures adherence to Plegridy treatment in the past 28 days, the number of missed injections, and reasons for discontinuation, if applicable. Refer to Section 16.5 and Section 16.6, Appendices 4 and 5.

Refer to Section 16.1 for the timing of assessments.

8.4. Data Sources

Except for instances where patient reported outcomes are entered directly into the EDC system by the patient, all data entered into the EDC system should be supported by source documentation maintained within the clinical site records.

8.5. Data Management

A CRO (IQVIA; Danbury, CT and Research Triangle Park, NC) will be responsible for administrative aspects of the study including, but not limited to, study initiation, monitoring, and management of SAE reports and data management. Before patients are

CONFIDENTIAL

The information contained herein may not be used, disclosed, or published without the written consent of Biogen MA Inc.

enrolled at each study site, the CRO will review study responsibilities with the Prescribing Physicians and other study site staff, as appropriate.

Patient information will be captured and managed by study sites on eCRFs by a web-based EDC tool developed and supported by IQVIA. All data will be collected and entered directly into IQVIA's EDC system. All participating sites will have access to the data entered regarding the individual site's own enrolled patients. All sites will be fully trained on using the EDC system, including eCRF completion guidelines and help files. Sites will be responsible for entering extracted patient data into a secure Internet-based EDC registry database via the eCRF. Investigators and site personnel will be able to access their account with a username and password. All eCRFs should be completed by designated, trained personnel or the study coordinator, as appropriate. The eCRF should be reviewed, electronically signed, and dated by the Principal Investigator or designee. All changes or corrections to eCRFs should be documented in an audit trail and an adequate explanation required.

8.6. Data Analysis

8.6.1. Description of Objectives

8.6.1.1. Primary Objective

The primary objective is described in Section [7.2](#).

8.6.1.2. Secondary Objectives

The secondary objectives are described in Section [7.3](#).

8.6.2. Description of Endpoints

8.6.2.1. Primary Endpoint

The primary endpoints are described in Section [8.1.1](#).

8.6.2.2. Secondary Endpoints

The secondary endpoints are described in Section [8.1.2](#).

8.6.3. Demography and Baseline Disease Characteristics

Demographic and baseline disease characteristics will be summarized overall. The demographic profile (age, sex, and race [where legally allowed]), relevant medical history, MS disease history, MS treatment prior to start of Plegridy, and concomitant medications and therapies used will be listed and summarized using appropriate descriptive statistics for categorical and continuous variables. Categorical variables will be summarized using frequencies and percentages. Continuous variables will be summarized using mean, SD, median, and maximum and minimum values. Two-sided

CONFIDENTIAL

The information contained herein may not be used, disclosed, or published without the written consent of Biogen MA Inc.

95% CIs will be used. In general, categorical data will be summarized using frequency and percentage, and continuous variables will be summarized using descriptive statistics (number, mean, SD, median, minimum, and maximum). For continuous variables, if the data are approximately normally distributed, then a 95% CI for the mean change will be calculated. If the data are not normally distributed, then the interquartile range will be presented with the median. All analyses will be conducted using a two-sided test and a significance level of 0.05. Due to the inherent differences in Plegridy-naïve patients and those who had exposure to Plegridy prior to study enrollment, analyses will be conducted separately for these two groups. The definition of Plegridy-naïve will be described in the SAP.

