
Study Size:
	
In Version 3.0 of this protocol, approximately 1600 patients across approximately 160 participating sites in the United States (US), European Union (EU), Australia, and sites participating in Study 105MS302 and 105MS303 in other countries were planned to be enrolled. In January 2017, following a decision by Biogen to limit enrollment to approximately 1100 patients, a Protocol Clarification Letter was sent to all study sites providing official notification that enrollment into the study should be stopped. The current target sample size is expected to provide acceptable precision around the estimates of the proportion of patients experiencing SAEs and ensure a reasonable likelihood of observing rare AEs over a 5-year period. The target sample size will also provide acceptable precision around the overall effectiveness endpoint of the proportion of patients with no evidence of disease activity clinically (cNEDA), which is defined as having no relapses and no disability progression.

Data Analysis:
	
Statistical analyses will be based on all patients who enroll in the study and receive at least one within-study dose of Plegridy. Analyses will be conducted separately for patients newly-prescribed Plegridy (Plegridy-naïve) from those who have previous exposure to Plegridy prior to study enrollment (Plegridy-experienced). Statistical analyses will generally be descriptive and exploratory in nature. No formal statistical hypothesis testing is planned.
 
Ninety-five percent confidence intervals (95% CIs) for the incidence and incidence rate point estimates will be calculated using the negative binomial distribution and the Poisson distribution, respectively. Analyses of continuous endpoints may include summaries of values over time, change from baseline over time, shift tables, and/or summaries of worst post-baseline values.
 
The proportion of patients with cNEDA will be calculated over time (e.g., Baseline to Year 1, Baseline to Year 2, etc.) as well as

CONFIDENTIAL

The information contained herein may not be used, disclosed, or published without the written consent of Biogen MA Inc.

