Longitudinal evaluation of continuously measured secondary endpoints (e.g., EQ-5D-3L and FLS) may be performed using a linear regression model to evaluate the long term experience (e.g. change over time) of patients regarding these measures while on Plegridy. Categorical outcomes on healthcare resource consumption, treatment adherence, [REDACTED] and Plegridy prescription and utilization patterns will be summarized using frequencies and percentages. If necessary, a 95% CI based on binomial distribution might be provided for some of the categorical variables like patient adherence.

FLS-VAS includes the patients' ratings of effectiveness and satisfaction of controlling FLS with prophylactic regimens. The ratings will be summarized by mean (SD) and median (maximum and minimum). Changes of FLS-VAS ratings over time will also be summarized by mean (SD) and median (maximum and minimum). The changes of FLS-VAS ratings over time will be tested using a Wilcoxon rank-sum test. Longitudinal evaluation of FLS-VAS ratings using a linear regression model may be performed to evaluate patients' long-term experience (e.g., change over time) with the effectiveness and satisfaction of prophylactic regimens to control FLS while receiving Plegridy.

[REDACTED]

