8.6.6. Interim Analyses

At a minimum, interim analyses are planned after at least 250 patients have completed one year of follow-up and annually thereafter.

Data from interim analyses will be submitted, at minimum, as abstracts to relevant congresses.

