8.6.7. Sample Size Considerations

While no formal statistical hypotheses are being tested in this descriptive observational study, 1100 patients newly or currently prescribed with Plegridy are being targeted for enrollment. All patients will be followed for up to five years, and follow-up is planned regardless of whether patients discontinue treatment with Plegridy. Because this is a long-term observational program, a sample size of 1100 patients was chosen to ensure a reasonable likelihood of observing rare AE events over a 5-year period and to provide informative CIs for SAE incidence and incidence rate point estimates. Based on the withdrawal/discontinuation rates observed in the Plegridy Phase III clinical trial (Study

CONFIDENTIAL

The information contained herein may not be used, disclosed, or published without the written consent of Biogen MA Inc.

105MS301, 1-year) and prior Biogen observational studies, it is expected that approximately 3520–3960 person-years of follow-up will accrue.

With a sample size of 1100 patients, the probability of observing an event with an incidence rate of 0.10% (1/1000 persons) will be approximately 67%; the probability of observing an event with an incidence rate of 0.09% (90/100,000 persons, or 1/1111 persons) will be approximately 63%; the probability of observing an event with an incidence rate of 0.08% (80/100,000 persons, or 1/1250 persons) will be approximately 59%; and the probability of observing an event with an incidence rate of 0.054% (54/100,000 persons, or 1/1851 persons) will be approximately 48%.

For the co-primary endpoint of cNEDA, assuming a dropout rate up to 20%, a sample size of 1100 patients, and an expected 68.4% of patients free from clinical disease activity at the end of one year (Study 105MS301, 1-year), a two-sided 95% CI for the observed proportion of patients free from measured clinical disease activity at the end of one year using large sample normal approximation will extend 0.027 to 0.031 from the observed proportion for an expected proportion of 0.684.

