The information contained herein may not be used, disclosed, or published without the written consent of Biogen MA Inc.

Section 2: Research question	Yes	No	N/A	Section Number
2.1.3 The target population? (i.e. population or subgroup to whom the study results are intended to be generalised)				7.1
2.1.4 Which hypothesis(-es) is (are) to be tested?				8.6.5.3, 8.6.5.4
2.1.5 If applicable, that there is no a priori hypothesis?				

Comments:

--

Section 3: Study design	Yes	No	N/A	Section Number
3.1 Is the study design described? (e.g. cohort, case-control, cross-sectional, new or alternative design)				6.1
3.2 Does the protocol specify whether the study is based on primary, secondary or combined data collection?				8.7
3.3 Does the protocol specify measures of occurrence? (e.g. incidence rate, absolute risk)				8.7.4.2
3.4 Does the protocol specify measure(s) of association? (e.g. relative risk, odds ratio, excess risk, incidence rate ratio, hazard ratio, number needed to harm (NNH) per year)				8.7.5.4
3.5 Does the protocol describe the approach for the collection and reporting of adverse events/adverse reactions? (e.g. adverse events that will not be collected in case of primary data collection)				10

Comments:

--

Section 4: Source and study populations	Yes	No	N/A	Section Number
4.1 Is the source population described?				8.2.4
4.2 Is the planned study population defined in terms of:				
4.2.1 Study time period?				8.2.3
4.2.2 Age and sex?				8.2.1.1

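### Section 8.6.3 puts all analyses under a two-sided 0.05 test and Section 8.6.5.4 orders a test of FLS-VAS change, while the abstract and Section 8.6.7 say no formal testing is planned

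*Protocol*

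**What the plan says.** The protocol takes two positions on inference.

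**Descriptive.** The abstract (Data Analysis) says "Statistical analyses will generally be descriptive and exploratory in nature" and then "No formal statistical hypothesis testing is planned". Section 8.6.7 opens with "While no formal statistical hypotheses are being tested in this descriptive observational study".

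**Testing.** Section 8.6.3 says "All analyses will be conducted using a two-sided test and a significance level of 0.05". The sentence stands under demography, but its wording covers every analysis. Section 8.6.5.4 then says "The changes of FLS-VAS ratings over time will be tested using a Wilcoxon rank-sum test". That instruction is mandatory, whereas the regression mentioned beside it is optional. In the ENCePP checklist (Annex 2), the item "2.1.4 Which hypothesis(-es) is (are) to be tested" is ticked Yes with reference to Sections 8.6.5.3 and 8.6.5.4, and item 2.1.5, on having no a priori hypothesis, is marked N/A.

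Three further facts bear on the size of the problem:
- Section 8.3.7 says of the FLS-VAS: "This patient-reported assessment includes two VAS ratings".
- Section 8.6.3 has Plegridy-naïve and Plegridy-experienced patients analysed separately.
- Section 8.6.6 says "interim analyses are planned after at least 250 patients have completed one year of follow-up and annually thereafter", with interim data going to congresses as abstracts.

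**The concern.** An SAP author cannot follow both positions. Under Sections 8.6.3 and 8.6.5.4, an FLS-VAS change with p below 0.05 is significant at the protocol's stated level. Under the abstract and Section 8.6.7, the same p-value is descriptive. Change in FLS-VAS over time is a listed secondary endpoint (Section 8.1.2), and Section 8.6.5.4 puts no nominal or exploratory label on the test. The choice of wording would therefore fall to whoever writes the report or, sooner, the annual congress abstract.

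The 0.05 level also suggests an error rate that the plan does not deliver. The test is not tied to a contrast or a time point, and there are at least two ratings and two groups to test.

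**Working it through.** **1. The plan's own figure.** Section 8.6.7 gives a 95% CI half-width of 0.027 to 0.031 for one-year cNEDA, with p = 0.684, N = 1100 and dropout up to 20%. The formula is 1.96 × √(p(1−p)/n).
- n = 1100: 1.96 × √(0.684 × 0.316/1100) = 0.0275
- n = 880: 1.96 × √(0.684 × 0.316/880) = 0.0307

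The figure reproduces. The co-primary precision rests on interval estimation alone, so no test at 0.05 underlies the sample size.

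**2. Which analyses the 0.05 level reaches.** Section 8.6.4.2 (SAEs) and Section 8.6.5.3 (cNEDA) prescribe estimates with 95% CIs and state no null value. The only significance test ordered by name is the FLS-VAS test.

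**3. How many FLS-VAS tests.** The protocol does not say.
- Low case, one time point: 2 ratings × 2 groups = 4 tests.
- High case, every post-baseline visit against baseline: Section 8.2.4.7 implies 4 visits in Year 1 and 8 in Years 2-5, so 2 × 2 × 12 = 48 tests. The abstract's list of Year 1 months (3, 6, 12) gives 2 × 2 × 11 = 44.

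**4. Chance of at least one false positive if each test has true size 5%.** For k independent tests this is 1 − 0.95^k. The correlated figures are simulated and assume independent groups. The four-test case uses the stated correlation between ratings; the 44-48 case uses the stated correlation across visits and 0.7 between ratings.

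| Tests | Independent | Correlated (assumed) |
|---|---|---|
| 4 | 1 − 0.95^4 = 18.5% | about 17% at 0.5; 15% at 0.8 |
| 44 | 1 − 0.95^44 = 89.5% | about 80% at 0.3; 70% at 0.5; 48% at 0.8 |
| 48 | 1 − 0.95^48 = 91.5% | about 82% at 0.3; 72% at 0.5; 49% at 0.8 |

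**5. Size of the test actually ordered.** A rank-sum test treats its two samples as independent. If it compares a visit with baseline in the same patients, with within-patient correlation r, its approximate size is 2 × (1 − Φ(1.96/√(1−r))).
- r = 0.3: 1.96/√0.7 = 2.34, size 1.9%
- r = 0.5: 1.96/√0.5 = 2.77, size 0.6%

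For four independent tests of that size, the chance of any false positive is 1 − (1 − 0.0191)^4 = 7.4% at r = 0.3 and 1 − (1 − 0.0056)^4 = 2.2% at r = 0.5. For 44-48 tests, simulated with ratings correlated 0.7 and changes from baseline correlated 0.5 across visits, it is about 40-42% and 15-16%.

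**6. Reading.** Depending on choices the protocol leaves open, the family-wise rate runs from about 2% to about 91%. None of these cases is fixed by the text.

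**The case against.** The strongest reply is that this is loose wording. The abstract and Section 8.6.7 exclude only *formal* testing, and the abstract calls the analyses *generally* descriptive and exploratory. A nominal FLS-VAS p-value can live under that label. The 0.05 sentence follows a remark on two-sided 95% CIs and reads as boilerplate. The checklist is an annex that prescribes no analysis. Time points, hierarchy and multiplicity handling for a secondary patient-reported outcome are commonly left to the SAP.

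Much of this stands. The missing multiplicity procedure is not the point here. Three stronger inferences a reader might draw are also not supported:
- *Dozens of tests at full 5% size, with error around 14 times the stated level.* The 44-48 count assumes a baseline comparison at every visit, and the size of the ordered rank-sum test falls well below 5% when the same patients are compared. The FLS-VAS is also waived when symptoms are absent (Sections 8.3.2 and 8.3.7), so overlap with baseline may be partial and the true size may lie in between.
- *Further inflation from annual interim looks.* Section 8.6.6 does not say which analyses are repeated, and any figure would need an assumed number and spacing of looks.
- *An undermined co-primary result.* The sections on SAEs and cNEDA order only estimates with intervals.

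What the reply does not remove is the conflict between the statements. Section 8.6.3 carries no qualifier to match the word formal, and the FLS-VAS test is required. An SAP cannot settle this without departing from one part of the protocol.

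**Conclusion.** The contradiction is real and stands in the protocol's own words. Its reach is limited to how secondary FLS-VAS results may be described, in the final report and in interim abstracts.

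The false-positive rate cannot be stated as one number. The figure of about 17-19% applies to four tests of true 5% size with correlation between ratings of 0 to 0.5. It is higher if each visit is tested, and much lower if the rank-sum test is applied to the same patients at two visits. What can be concluded is that 0.05 does not describe the error rate of this analysis and may err in either direction. The point should be corrected because the repair is cheap and follows the sponsor's stated descriptive intent.

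**What to change.** 1. In Section 8.6.3, replace the 0.05 sentence with: *No formal hypothesis tests are planned; estimates are presented with two-sided 95% CIs, and any p-value, at interim or final analysis, is nominal, unadjusted for multiplicity and exploratory.*
2. In Section 8.6.5.4, replace the rank-sum test with the within-patient change in each FLS-VAS rating and its 95% CI, by visit and exposure group, with the number of patients contributing both ratings. This respects the pairing and shows the size of the change.
3. In the ENCePP checklist, align items 2.1.4 and 2.1.5 with the descriptive position: N/A for the first and Yes for the second.

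The cost is wording in two sections and two checklist entries, with no new data or patients. The small downside is that the sponsor gives up describing FLS-VAS changes as statistically significant.
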